## **3. Study Methods**

### ***Trial design***

This is a 2-arm randomized controlled trial of free-living, generally healthy men and women and living in the State College, PA area. In a 1:1 ratio, participants will be randomized to the intervention arm or the control arm. The intervention group will receive a 12-week culinary focused nutrition education program, The control group will receive standard low-intensity

care. Outcome measures will be assessed at baseline and 15 weeks  $\pm$  7 days in both groups. Participants in the intervention group will receive culinary focused nutrition education based on MyPlate with an emphasis on taste and enjoyment of healthy foods. Using herbs and spices to flavor foods will be the emphasis. The intervention will be delivered in an online format with online content delivery by email via REDCap. The intervention will consist of eight modules. Modules one to four will be provided during the first month. Modules four to eight will be provided during months 2 and 3. The control group will represent standard low intensity care.

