#### ***Sample size estimate***

Limited comparable data exist to inform a power calculation; therefore, 50 participants (25 per group) will be recruited based on convenience.

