**6. Hypothesis Testing**

For all primary analyses, the between-group difference in the change from baseline for all outcome variables except program acceptability and satisfaction will be assessed. A sensitivity analysis will be conducted to examine between-group differences in endpoint means for continuous outcomes. Between-group differences in program acceptability and satisfaction will be assessed with chi-square test for proportions.

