## 7. Statistical Analyses

Statistical model assumptions will be evaluated and confirmed prior to analyses for hypothesis testing being conducted, and where necessary transformations will be made to meet assumptions for normality. All primary analyses will follow intent-to-treat principles. The primary analyses will assess between-group change from baseline for all continuous repeated-measure outcome variables using linear regression (PROC GLM). Sex effects will be examined by including sex  $\times$  group as a fixed effect. If the main effect of sex  $\times$  group is non-significant, sex  $\times$  group will be removed from the model. As a sensitivity analysis, between-group differences in endpoint means will be assessed using linear mixed models (PROC MIXED). Group assignment will be modeled as a fixed effect and study visit will be modeled as a repeated effect. When a significant group-by-visit interaction is detected, post hoc testing will be conducted, and the Tukey-Kramer method will be used to adjust for multiple comparisons. Selection of model covariance structures will be based on optimizing fit statistics (evaluated as the lowest Bayesian information criterion). Between-group differences in variables assessed only at endpoint (i.e., program acceptability and satisfaction) will be assessed with chi-square test for proportions. Data from continuous repeated-measure variables will be presented as least squared means  $\pm$  SEM. Data from categorical endpoint variables will be presented as frequency and percentage of sample. Non-normally distributed data will be presented as geometric mean (95% confidence interval). Data from post-hoc testing will be presented as the pairwise mean difference and 95% confidence interval with the Tukey-Kramer adjusted P value. Statistical significance will be set at  $p<0.05$ . All analyses will be conducted with SAS 9.4 (SAS Institute, Cary, NC).

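### The p-value of a weak sex × group test decides which primary model is reported, and so what the HEI-2015 group effect estimates

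*SAP*

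**What the plan says.** Section 6 of the SAP (Hypothesis Testing) sets the target for all primary analyses: "the between-group difference in the change from baseline for all outcome variables except program acceptability and satisfaction will be assessed". Section 7 (Statistical Analyses) carries this out for every continuous outcome, HEI-2015 included, by linear regression in PROC GLM.

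Section 7 then adds to that model: "Sex effects will be examined by including sex" × group, as a fixed effect. The next sentence opens "If the main effect of sex" × group and says that, when this is non-significant, sex × "group will be removed from the model". The significance level is 0.05. On presentation it says: "Data from continuous repeated-measure variables will be presented as least squared means", with their standard errors. No weighting over sex is stated.

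A PROC MIXED analysis with group and visit, and no sex term, is labelled a sensitivity analysis.

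On the sample, Section 3 says that "50 participants (25 per group) will be recruited based on convenience" and that the trial enrols "generally healthy men and women". It gives no expected sex split, and its randomization paragraph states no stratification by sex.

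**The concern.** The primary question is the overall group difference in HEI-2015 change. Under the Section 7 rule, a preliminary test decides which model answers it. If the interaction is dropped, the group effect is the pooled difference. If it is kept, the group contrast of least squares means gives each sex weight one half whatever the sex mix. On another reading, sex-specific effects would be reported. The SAP does not say which.

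The choice is made outcome by outcome, so one results table can hold two different quantities. In a trial this small the choosing test mostly reflects chance. The group estimate and the interaction estimate are also correlated when the sexes are unequal. Selecting on a significant interaction therefore distorts the group test in the outcomes where the term stays.

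**Working it through.** **Inputs.** From the SAP: 25 per arm and significance at 0.05. Assumed, because the SAP gives no figures: two-sided tests, outcome SD of 1 (effects in SD units of change), the same sex mix in both arms (12, 15, 18 or 20 of 25 of one sex), and a model with group, sex and sex × group (46 residual df). The SAP has no power calculation to reproduce.

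**1. Precision and power of the interaction test.** With n₁ and n₂ of each sex per arm, SE(interaction) = √(2/n₁ + 2/n₂). The pooled group difference has SE = √(2/25) = 0.283.

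- 12/13: √(2/12 + 2/13) = 0.566, twice the pooled SE
- 18/7: √(2/18 + 2/7) = 0.630
- 20/5: √(2/20 + 2/5) = 0.707, 2.5 times the pooled SE

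Power for a 0.5 SD interaction (noncentral t, 46 df) is 13.9%, 12.2% and 10.6%. An interaction of about 1.6 SD (even split) to 2.0 SD (80/20) would be needed for 80% power.

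**2. How far apart the two estimates are.** Let p be the share of one sex and e₁, e₂ the sex-specific effects.

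- Pooled: p·e₁ + (1 − p)·e₂
- Equal-weight: (e₁ + e₂)/2
- Difference: (0.5 − p)·(e₁ − e₂), that is (0.5 − p) times the estimated interaction

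The term stays only if the estimated interaction exceeds about 2.013 standard errors. With residual SD near 1, the gap in kept trials is then at least about 0.22 × 2.013 × 0.630 = 0.28 SD at 18/7, and 0.30 × 2.013 × 0.707 = 0.43 SD at 20/5.

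**3. Why the group test is distorted.** The correlation between the equal-weight group estimate and the interaction estimate has absolute value |n₁ − n₂|/25: 1/25 = 0.04, 5/25 = 0.20, 11/25 = 0.44 and 15/25 = 0.60.

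**4. The rule under the null** (400,000 simulated trials per column):

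| Of one sex, per arm of 25 | 12 (48%) | 15 (60%) | 18 (72%) | 20 (80%) |
|---|---|---|---|---|
| Term kept | 5.0% | 5.0% | 5.0% | 5.0% |
| Group test rejects, kept trials | 6.0% | 8.0% | 17.1% | 26.1% |
| Same, exact bivariate t | 6.3% | 8.3% | 16.6% | 26.1% |
| Plain group test, same trials | 4.7% | 4.7% | 5.3% | 4.9% |
| Mean absolute departure from pooled, kept trials (SD) | 0.026 | 0.132 | 0.317 | 0.487 |
| SE ratio, kept model to plain | 0.95 | 0.97 | 1.06 | 1.19 |
| Overall type I error | 5.0% | 5.2% | 5.6% | 6.1% |

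Drawing sex at random within each arm (50%, 72%, 80%) gives overall error of 5.1%, 5.7% and 6.2%.

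**5. When an interaction exists.**

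- With a 0.5 SD interaction and a pooled effect of zero, the rule rejects in 6.3% (18/7) and 7.3% (20/5), against 4.7% and 4.8% for a plain test.
- With an effect of 0.8 SD in the larger sex and none in the other, at 18/7, the pooled effect is 0.72 × 0.8 = 0.58 SD and the equal-weight effect is 0.40 SD. The term is kept in 24% of trials. Overall power falls from 49% for the plain test to 40% under the rule.

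**6. Other readings of a kept term** (13/12 to 20/5, null). If the coefficient for a reference sex is read as the group effect, overall type I error is 6.7–7.6%. If either sex-specific effect may be claimed, it is about 8.2%.

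**7. Outcomes affected by chance.** HEI-2015 total 1, food groups 9, sugars/sodium/saturated fat 3, weight 1, waist 1, blood pressure 4, PWV 1, glucose 1 and HbA1c 1 make 22, leaving out the HEI components and the lipids. 22 × 0.05 = 1.1 outcomes would keep the term with no interaction anywhere.

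**The case against.** The strongest reply is that the effect is small. Overall type I error is at most about 6.1%, and under the null the rule changes the group verdict, compared with a plain test, in only 0.07%, 0.3%, 0.8% or 1.3% of trials across the four sex mixes. The large figures need both a 5% event and an assumed imbalance. This stands, and it limits the severity. It does not settle what the estimate means for the outcomes where the term stays.

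Equal weighting is inferred from a software default, and sex-specific reporting is equally plausible. That is fair, but the other readings give larger overall error, and leaving them open is part of the defect.

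The calculations assume a sex main effect, which the SAP does not name. Coded literally, the term is a 2-df test of sex within group, which also picks up ordinary sex differences. Rejection in kept null trials is then 13% (18/7) and 20% (20/5), with overall error of 5.4% and 5.8%. With a 0.5 SD sex main effect the term is kept in 21–32% of trials, so the count of 1.1 no longer applies, although overall error is still 4.9–5.6%. The size depends on the coding. The data-dependent choice does not.

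The PROC MIXED group-by-visit contrast, with two visits and complete data, equals the pooled difference in change and is run regardless of the sex test. A discrepancy would therefore be visible, but as a sensitivity analysis it does not replace the primary result.

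Finally, the rule is prespecified, the analysis is masked and the trial is a pilot. Prespecification removes analyst discretion but not dependence on the data, and the SAP still sets a superiority framework at p<0.05.

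**Conclusion.** The concern holds. The primary group effect, for HEI-2015 and every other continuous outcome, has no fixed meaning until the sex × group p-value is known, and that test has 11–14% power for a 0.5 SD interaction. The harm is concentrated in outcomes that keep the term. It ranges from negligible near an even split to 26% rejection under the null and a mean departure of 0.49 SD at 80/20. Average type I error is only slightly raised.

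These sizes rest on the assumed sex mix, a sex main effect in the model, equal-weight least squares means and no dropout. The change should be made before unmasking, but the issue does not undermine the trial.

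**What to change.** Prespecify the primary model for each continuous outcome without sex × group, and remove no term on its p-value. A sex main effect may be included if the SAP says so in advance. Fit group, sex and sex × group (1 df) in a separate exploratory model. Report the interaction estimate with its 95% CI whatever its p-value, and leave the primary estimate unchanged. Call the term an interaction, not a main effect.

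The cost is a change of wording in Section 7 and one additional exploratory model per outcome. No new data are needed.

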#### ***Randomization method, allocation concealment, blinding***

Group assignment will be randomized at the individual level. The allocation sequence will have block sizes of 4 and 8 and be computer-generated by a person not involved in recruitment or data collection. The person will upload it to REDCap. REDCap will be used to ensure allocation concealment. At baseline testing, the study coordinator will use the randomization module in REDCap to reveal the participant's randomization. Participants and study staff involved in recruitment and data collection will not be blinded due to the nature of the intervention. Statistical analyses will be performed using a masked dataset (e.g., group labels A/B), with unblinding occurring after completion of the primary analyses.

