#### ***Timing of outcome assessment***

Outcomes will be assessed during the single-day baseline and endpoint visits. The endpoint visit will occur 15 weeks  $\pm$  7 days following the baseline visit.

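### With only two visits, choosing the sensitivity model's covariance by lowest BIC gains almost nothing and can misstate the endpoint standard error; the unstructured matrix should be fixed in advance

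*SAP*

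**What the plan says.** SAP section 7 plans two analyses of each continuous outcome.

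- **Primary:** between-group change from baseline for "continuous repeated-measure outcome variables using linear regression (PROC GLM"). This is a regression on change scores and involves no covariance structure.
- **Sensitivity:** "between-group differences in endpoint means will be assessed using linear mixed models (PROC MIXED"), in which "study visit will be modeled as a repeated effect". For this model: "Selection of model covariance structures will be based on optimizing fit statistics (evaluated as the lowest Bayesian information criterion"). No candidate structures are listed and no default is named.

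Under Timing of outcome assessment: "Outcomes will be assessed during the single-day baseline and endpoint visits". The repeated factor therefore has two levels. Under Sample size estimate, "50 participants (25 per group) will be recruited based on convenience".

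Section 7 makes post hoc comparisons conditional on a significant group-by-visit interaction and adjusts them by Tukey-Kramer. Section 6 describes the sensitivity analysis simply as a comparison of endpoint means, with no such condition.

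**The concern.** Selecting a covariance structure is worthwhile when many visits make the full matrix expensive to estimate. With two visits that matrix is two variances and one covariance, and every simpler structure is a special case of it.

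The selection also has a cost. Compound symmetry (CS) and independence (VC) both force one variance on the two visits. If the visits truly differ in spread, the endpoint comparison then uses a variance that belongs partly to baseline. Its standard error is too small when the endpoint is the more variable visit and too large when it is the less variable one. BIC penalises the extra variance parameter, so a sample of 50 often will not reveal the difference.

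At stake is the reliability of the planned sensitivity analysis of endpoint means, not the primary result.

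**Working it through.** **Inputs.** From the SAP: two visits, 25 per arm, 1:1 allocation, significance at 0.05. Assumed, because the SAP is silent: two-sided tests, complete data, within-person correlation 0.1 to 0.7, endpoint/baseline SD ratio 0.8 to 1.35 common to both arms, and candidates VC, CS and unstructured (UN), or CS and UN only. The SAP states no error rate or precision figure to reproduce.

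**Criterion.** With a saturated group-by-visit mean there are 50 − 2 = 48 residual degrees of freedom. Let *a* and *b* be the residual variances at baseline and endpoint, *d* their covariance, and *s* = (*a* + *b*)/2. Up to a constant, minus twice the restricted log-likelihood is:

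- VC: 96 ln *s* (1 parameter)
- CS: 48 ln(*s*² − *d*²) (2 parameters)
- UN: 48 ln(*ab* − *d*²) (3 parameters)

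BIC adds ln 50 = 3.91 per parameter. UN therefore beats CS only if 48 ln[(*s*² − *d*²)/(*ab* − *d*²)] exceeds 3.91. That is a one-degree-of-freedom likelihood-ratio test at p = 0.048.

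**How often the pooled variance survives.** Take SDs of 1 and 1.25, so *a* = 1, *b* = 1.5625, *s* = 1.28125 and *d* = 1.25 × correlation. Putting these population values into the statistic, beside the simulated frequency of CS with candidates CS and UN:

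| Correlation | Statistic (threshold 3.91) | CS chosen |
|---|---|---|
| 0.3 | 48 ln(1.5010/1.4219) = 2.60 | 64% |
| 0.5 | 48 ln(1.2510/1.1719) = 3.14 | 57% |
| 0.7 | 48 ln(0.8760/0.7969) = 4.54 | 43% |

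At SD ratios of 0.9 or 1.1 and the same correlations, CS is chosen in 83% to 89% of trials. At correlation 0.9 with ratio 0.8 or 1.25, this falls to 7%.

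**Effect on the endpoint standard error.** The correct value is √(2*b*/25). CS and VC use √(2*s*/25). The ratio is √(*s*/*b*):

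- SD ratio 1.25: √(1.28125/1.5625) = 0.91
- SD ratio 0.8: √(0.82/0.64) = 1.13

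In simulation, when CS is picked, the endpoint standard error is 0.88 to 0.95 of the true value if the endpoint is more variable (ratios 1.1 and 1.25). It is 1.05 to 1.12 times the true value if the endpoint is less variable (ratios 0.9 and 0.8). When UN is picked the error runs mildly the other way, so the average over the procedure is smaller.

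**Results averaged over selection** (40,000 trials per setting, no true effect, SD ratio different from 1):

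| Procedure | Endpoint SE / true SE | Type I error, unadjusted and ungated |
|---|---|---|
| BIC among VC, CS, UN | 0.93 to 1.08 | about 3.4% to 6.7% |
| BIC among CS, UN | 0.95 to 1.05 | about 4.0% to 6.2% |
| UN fixed in advance | about 0.995 | about 5% |

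**Equal SDs.** With CS and UN as candidates, UN is picked about 5% of the time and the endpoint standard error is unaffected. If VC is a candidate, it is picked in 89%, 71% and 43% of trials at correlation 0.1, 0.2 and 0.3, but the endpoint standard error still averages about 1.00 of the true value.

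**Group-by-visit test.** The variance of change is *a* + *b* − 2*d* under UN and 2*s* − 2*d* under CS. These are identical, so with complete data the test differs only if an independence structure is picked. With equal SDs and correlation up to 0.3, VC selection makes this standard error up to about 5% too large and the test rejects at about 4.2% to 4.4% (4.0% to 4.5% across repeat runs).

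**Missing endpoints.** A smaller check with 16% of endpoints missing (700 trials in each of four settings) gave a selected-to-UN standard error ratio of 0.95 to 1.06, the same pattern.

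**The case against.** The strongest reply is that a lowest-BIC rule is a recognised, prespecified procedure, applied here only to a sensitivity analysis in a pilot of convenience size. Most of that stands, and it is why the point is minor. Several particulars also stand.

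- **No stated reason for unequal SDs.** HEI-2015 is scored the same way at both visits from three recalls, and nothing in the SAP implies a different spread when the program has no effect. The distortion is conditional.
- **The gate.** If the endpoint contrast is tested only after a significant interaction and with Tukey-Kramer adjustment, its false-positive rate is 0.1% to 0.9% under BIC selection and 0.1% to 0.7% under fixed UN. The largest difference is about 0.25 percentage points. The 3.4% to 6.7% range applies only if the contrast is read without the gate and adjustment, as section 6 allows.

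A reader might also infer three stronger things that the SAP does not support.

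- **That the structure is chosen after unblinding.** The SAP has analyses done on a masked dataset, "with unblinding occurring after completion of the primary analyses". It does not say that the sensitivity models are run unmasked, and the BIC rule does not depend on knowing which group is which.
- **That frequent misselection means wrong endpoint standard errors.** The highest rates (89%, 71%, 43%) arise with equal SDs and VC as a candidate, where the endpoint standard error is right.
- **That selection is stated to be outcome by outcome.** This is the natural reading, since each outcome has its own model, but it is an inference.

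What remains is that the rule offers almost no gain to set against a conditional cost.

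**Conclusion.** The point holds as a minor, conditional one. With two visits, BIC selection is unnecessary. If the SDs at the two visits differ, it can shift the sensitivity standard error of the endpoint difference by about −7% to +8% on average, and by about 5% to 12% in trials where compound symmetry is wrongly kept. Equal SDs leave that standard error intact.

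The size rests on the assumed SD ratio, correlation and candidate set, on complete data, and on two-sided tests. It does not reach the primary analysis of change. It leaves the group-by-visit test alone unless an independence structure is picked or, slightly, endpoints are missing.

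**What to change.** Replace the BIC sentence in SAP section 7 with: *An unstructured covariance for the two visits will be used for all continuous outcomes; a simpler structure will be used only if the unstructured model fails to converge.*

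Kenward-Roger degrees of freedom may be named as well but are optional. The cost is one sentence and at most two extra covariance parameters against 48 residual degrees of freedom. In return a data-driven step is removed from every sensitivity model.
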